6.3.1.2 Alpelisib/placebo

Management of severe or intolerable adverse reactions requires dose reduction, temporary interruption, and/or discontinuation of alpelisib therapy. A maximum of 2 dose reductions will be allowed, after which the patient will be discontinued from treatment with alpelisib/placebo. Dose reduction should be based on the worst preceding toxicity.

Please refer to [Table 6-2](#) and [Table 6-3](#) for guidance.

Table 6-2 Dose reduction sequential steps for alpelisib/placebo

Alpelisib/placebo dose level	Dose and schedule	Number of tablets & strength
Starting dose	300 mg/day continuously	1 x 200 mg tablet and 2 x 50 mg tablet
Dose level -1	250 mg/day continuously	1 x 200 mg tablet and 1 x 50 mg tablet
Dose level -2	200 mg/day continuously	1 x 200 mg tablet

Recommendations for dose reduction or dose interruption of alpelisib/placebo in the management of adverse reactions are summarized in [Table 6-3](#). No dose modification for fulvestrant is permitted. Clinical judgment of the treating physician, including confirmation of lab values if deemed necessary, should guide the management plan of each patient based on individual benefit/risk assessment.

However, treatment must be discontinued as indicated in [Table 6-3](#).

After treatment is resumed at a lower dose:

- If the same toxicity recurs with the same severity, then the next treatment re-initiation must resume at a lower dose irrespective of duration.
- Once the alpelisib/placebo dose has been reduced, no re-escalation will occur, even upon resolution of AE.

If a patient requires a dose delay of alpelisib/placebo for > 28 days from the intended day then the patient must be discontinued from alpelisib/placebo, but may continue on fulvestrant. All scheduled assessments will continue to be performed. If fulvestrant is held for more than 35 days since a planned injection, then fulvestrant should be permanently discontinued. The patient may continue on alpelisib/placebo at the discretion of the investigator until study completion, in which case all scheduled assessments will continue to be performed.

Table 6-3 Criteria for interruption and re-initiation of alpelisib/placebo treatment

Dose Modifications for alpelisib/placebo as specified below. Fulvestrant may be continued while alpelisib/placebo dose is being held, at the investigators discretion, and as specified in Section 6.3.1	
Worst toxicity -CTCAE Grade (value)	Dose Modifications for alpelisib/placebo

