Investigations (Fasting Plasma Glucose)	
Hyperglycemia (see also Section 6.3.2.1.3)	
	
Always consider consultation with a diabetologist and recommend/reinforce on lifestyle changes as per ADA, i.e. exercise and dietary advice (e.g. small frequent meals, low carb, high fiber, low process food intake, three macronutrient balanced meals and 2 optional small snacks rather than one large meal).
 
Note: this table provides dose management recommendations. The preferred option for treating alpelisib-induced hyperglycemia is metformin, given its wide availability and well characterized safety profile. However, in case of intolerance to or unavailability of metformin, investigator's judgment should be exercised and other insulin sensitizers such as SGLT2 inhibitors, thiazolidinediones or dipeptidyl peptidase-4 Inhibitors can be used.

Grade 1 (> ULN - 160 mg/dL) [> ULN - 8.9 mmol/L] For patients with baseline values between >ULN – 140 mg/dL (ULN – 7.7 mmol/L) this apply only for values > 140 mg/dL (7.7 mmol/L)	
Maintain dose level, and remind patient on lifestyle changes*.
 
 ● If FPG < 140 mg/dl, consider adding metformin as per guidance below or in cooperation with diabetologist ● If FPG 140-160 mg/dl, start/intensify metformin as per guidance below or in cooperation with diabetologist 
Metformin 500 mg once daily with dinner. If no gastrointestinal (GI) intolerance after several days, increase to 500 mg bid, with breakfast and dinner. If tolerated, increase to 500 mg with breakfast, and 1000 mg with dinner. If tolerated, 1000 mg bid with breakfast and dinner. If not tolerated, reduce to prior tolerated dose.
 
Monitor FPG as clinically indicated and at least weekly for 8 weeks, then continue checking at least every two weeks until FPG is within baseline values.

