Grade 2 (>160 - 250 mg/dL) [> 8.9 - 13.9 mmol/L]	
Maintain dose level and remind patient on lifestyle changes*, exclude confounding factors like e.g. urinary tract infection, consider consultation with a diabetologist and start oral-antidiabetic treatment, e.g. metformin 500 mg bid with breakfast and dinner. If no GI intolerance, increase to 500 mg with breakfast, 1000 mg with dinner. If tolerated, 1000 mg bid with breakfast and dinner. If not tolerated, reduce to prior tolerated dose. Titrate to the maximum tolerated dose over a period of 3 weeks. A second oral hypoglycemic agent may be initiated if needed.
 
If FPG is still rising on maximum tolerated dose of metformin or persistently >160mg/dl (>8.9 mmol/L, add an SGLT2 inhibitor if available, e.g. empagliflozin up to 25 mg (max. dose). Alternatively, an insulin-sensitizer, e.g. pioglitazone 30 mg (max. dose) can be added.
 
Monitor FPG as clinically indicated and at least weekly until FPG resolves to ≤ Grade 1
 
 ● If FPG does not resolve to ≤ Grade 1 within 21 days after institution of appropriate anti-diabetic treatment, reduce alpelisib/placebo by 1 dose level ● Continue with anti-diabetic treatment and check FPG at least weekly for 8 weeks, then continue checking at least every 2 weeks, alert treating physician if FPG>250mg/dl

Dose Modifications for alpelisib/placebo as specified below. Fulvestrant may be continued while alpelisib/placebo dose is being held, at the investigators discretion, and as specified in Section 6.3.1	
Worst toxicity -CTCAE Grade (value)	Dose Modifications for alpelisib/placebo

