Grade 3 (FPG > 250 - 500 mg/dL) [> 13.9 - 27.8 mmol/L]	
Omit alpelisib/placebo and confirm fasting status of the assessment. If non-fasting, re-check within 24 hours.
 
Regardless of fasting status, consider IV fluids if symptoms of hyperglycemia or signs of volume depletion.
 
Exclude confounding factors like e.g. urinary tract infection and consider consultation with a diabetologist.
 
Administer intravenous hydration and intervention for electrolyte/ketoacidosis/hyperosmolar disturbances as clinically appropriate. Start metformin and titrate as outlined for Grade 2, add insulin sensitizers (i.e. pioglitazone) or a SGLT2 inhibitor, if available, as outlined for Grade 2. Insulin may be used for 1-2 days until hyperglycemia resolves, however this may not be necessary in the majority of alpelisib-induced hyperglycemia given the short half-life of alpelisib.
 
Monitor FPG as clinically indicated and at least twice weekly until FPG resolves to \leq Grade 1.
 
 • If FPG resolves to \leq 160 mg/dL within 3-5 days, while off study treatment and on metformin, re-start alpelisib/placebo and reduce 1 dose level, continue with anti-diabetic treatment..A second and third oral hypoglycemic agent may be initiated concomitantly, if needed, in consultation with a diabetologist. Check FPG at least weekly for 8 weeks, then continue checking at least every 2 weeks, alert treating physician if FPG>250mg/dl • If FPG does not resolve to \leq 160 mg/dL within 3-5 days while off study treatment and on metformin, consult a diabetologist for management of diabetes is strongly recommended. • If FPG does not resolve to \leq 160 mg/dL within 21 days after institution of appropriate anti-diabetic treatment in cooperation with diabetologist and exclusion of confounding factors e.g. urinary tract infection, permanently discontinue patient from alpelisib/placebo treatment.

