Grade 4 (FPG > 500 mg/dL) [≥ 27.8 mmol/L]	
Omit alpelisib/placebo, confirm fasting status of the assessment. If non-fasting, re-check within 24 hours.
 
 • Regardless of fasting status, consider IV fluids. Exclude confounding factors like e.g. urinary tract infection. • Should consult with diabetologist, initiate or intensify medication with appropriate anti-diabetic treatment (see Grade 3), re-check within 24 hours. • If grade improves then follow specific grade recommendations • If FPG is confirmed at Grade 4 and confounding factors could be excluded, permanently discontinue patient from alpelisib/placebo.

Dose Modifications for alpelisib/placebo as specified below. Fulvestrant may be continued while alpelisib/placebo dose is being held, at the investigators discretion, and as specified in Section 6.3.1	
Worst toxicity -CTCAE Grade (value)	Dose Modifications for alpelisib/placebo
A diabetologist consultation should always be considered. For all grades : instruct patient to follow dietary guidelines according to local and/or institutional standards for management of diabetes mellitus (such as those provided by the American Diabetes Association) during the study, e.g. controlled carbohydrate intake, high fiber, low processed food intake; three macronutrient balanced meals and 2 small snacks rather than one large meal.	
* specific recommendations please see Section 6.3.2.1.3 .	
Thrombocytopenia	
Grade 1 (PLT < LLN - $75 \times 10^9/L$)	Maintain dose level
Grade 2 (PLT < $75 - 50 \times 10^9/L$)	
Grade 3 (PLT < $50-25 \times 10^9/L$)	Omit dose until resolved to \leq Grade 1, then: 
 • If resolved in \leq 7 days, then maintain dose level • If resolved in $>$ 7 days, then \downarrow 1 dose level
Grade 4 (PLT < $25 \times 10^9/L$)	Omit dose until resolved to \leq Grade 1, then \downarrow 1 dose level
Investigations (Renal)	
Serum creatinine	
< 2 x ULN	Maintain dose level
2 – 3 x ULN	Omit dose until resolved to \leq grade 1, then: 
 • If resolved in \leq 7 days, then maintain dose level • If resolved in $>$ 7 days, then \downarrow 1 dose level
Grade 3 (> 3.0 – 6.0 x ULN)	Permanently discontinue patient from alpelisib/placebo
Grade 4 (> 6.0 x ULN)	Permanently discontinue patient from alpelisib/placebo
Investigations (Hepatic)	
Isolated total Bilirubin elevation	

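### A true fasting Grade 4 glucose that improves within 24 hours can be read as allowing same-dose resumption with no restart threshold, a milder rule than for Grade 3

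*Protocol*

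**What the plan says.** Protocol Section 6.3.1.2 states the general principle: "Dose reduction should be based on the worst preceding toxicity". The grade column of Table 6-3 is likewise headed by worst toxicity.

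In the hyperglycemia part of Table 6-3:

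- **Grade 4 (FPG above 500 mg/dL).** Drug is omitted and fasting status is confirmed; a non-fasting sample is repeated within 24 hours. A separate bullet then applies to everyone: "Should consult with diabetologist, initiate or intensify medication with appropriate anti-diabetic treatment (see Grade 3), re-check within 24 hours". Next comes "If grade improves then follow specific grade recommendations". If Grade 4 is confirmed and confounders are excluded, the drug is stopped for good.
- **Grade 3 (above 250 to 500 mg/dL).** Drug is omitted and FPG is monitored at least twice weekly. If FPG is 160 mg/dL or less within 3 to 5 days off drug, the instruction is "re-start alpelisib/placebo and reduce 1 dose level, continue with anti-diabetic treatment". If 160 mg/dL is not reached within 21 days of appropriate treatment, with confounders excluded, the drug is permanently discontinued.
- **Grade 2 (above 160 to 250 mg/dL).** "Maintain dose level and remind patient on lifestyle changes". The only reduction is for failure to return to Grade 1 or better within 21 days of treatment.
- **Grade 1 (up to 160 mg/dL).** "Maintain dose level, and remind patient on lifestyle changes".

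Neither the Grade 1 nor the Grade 2 row contains a hold or a condition for restarting. Section 6.3.2.1.3 refers back to the table and adds no restart rule.

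**The concern.** The 24-hour value is taken with the drug withheld and anti-diabetic treatment started or intensified. An improved grade at that point does not show that the patient tolerates the earlier dose. The plan itself expects glucose to recover off drug: on the need for insulin, the Grade 3 row comments "however this may not be necessary in the majority of alpelisib-induced hyperglycemia given the short half-life of alpelisib".

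The rows to which the patient is sent were written for someone still taking the drug, so they never say when a held drug may restart. What is at stake is the safety of re-exposure after a fasting value above 500 mg/dL. There is also a consistency question, because two sites applying different parts of the same section could restart the same patient at different glucose levels and different doses.

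**Working it through.** The plan gives no figure to reproduce, so the check is a trace of the branches. The patient has a true fasting, unconfounded FPG above 500 mg/dL, drug on hold and treatment started. For each possible re-check value, the row reached is compared with what the Grade 3 recommendations would require at the same value.

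| Re-check FPG (mg/dL) | Row reached | Action under that row | Under the Grade 3 recommendations | Difference |
|---|---|---|---|---|
| up to 160 | Grade 1 | dose level kept | restart, one level lower | dose only |
| >160 to 250 | Grade 2 | dose level kept; reduce only if unresolved at 21 days | stay off drug | hold and dose |
| >250 to 500 | Grade 3 | Grade 3 rules | Grade 3 rules | none |
| >500, confirmed, no confounder | Grade 4 | permanent stop | not applicable | none |

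**What keeping the dose level means for a held drug.** Four other rows of Table 6-3 omit the drug until recovery and then use the same phrase: Grade 3 thrombocytopenia resolved within 7 days, creatinine 2 to 3 x ULN resolved within 7 days, Grade 2 bilirubin resolved within 14 days, and asymptomatic amylase/lipase of Grade 3 or worse resolved within 14 days. There it means resuming at the previous dose. Each of those rows also says how far the value must recover first. The Grade 1 and Grade 2 hyperglycemia rows do not.

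**The inversion.** Take two patients on 300 mg, both at 200 mg/dL off drug. One peaked between 251 and 500 mg/dL: that patient stays off drug until FPG is 160 mg/dL or less, then restarts at 250 mg. The other peaked above 500 mg/dL and came down to 200 mg/dL at the re-check: that patient is in the Grade 2 row and may be read as resuming 300 mg now.

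**Size of the dose difference (Table 6-2 levels of 300, 250 and 200 mg).**

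- From 300 mg: (300 − 250)/300 = 16.7%.
- From 250 mg: (250 − 200)/250 = 20.0%.
- At 200 mg there is no lower level, and Section 6.3.1.2 allows only two reductions, so the choice is to stay on drug or stop.

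**Reach.** Section 6.3.2.1.3 places typical onset in the first month of treatment. Enrollment closed on 21 July 2017 and Amendment 5 is dated 11 February 2020: 935 days, and 935/30.4375 = 30.7 months. The documents give no rate for Grade 4 hyperglycemia alone, so the number of affected patients cannot be calculated.

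**The case against.** The best defense is that the Grade 4 bullets form a confirmation step: a confirmed value stops the drug, and an unconfirmed one is managed at the grade actually found. On this view the general rule only tells the site which row to act on. It does not demand a reduction after every hold, as Grade 3 thrombocytopenia shows. The table describes its content as recommendations, Section 6.3.1.2 leaves each plan to clinical judgment, and the Grade 4 row calls for a diabetologist.

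Much of this stands. The texts can be read together, and a careful physician would probably not restart at 250 mg/dL. But a re-check made after treatment has begun is not a clean confirmation: a fall may reflect the hold and the treatment rather than a false initial reading. Judgment and consultation also supply no threshold, whereas the Grade 3 row does.

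Two stronger readings might be inferred, and neither is supported. One is that the table leaves the restart dose blank. Its own usage of the phrase points to the same dose; what is missing is the threshold. The other is that the table expressly orders full-dose resumption after Grade 4. No row says so; the routing permits it.

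**Conclusion.** The point holds, and it is minor. For a true fasting, unconfounded Grade 4 value that falls to Grade 1 or 2 at the re-check, Table 6-3 permits resumption at the same dose without a restart threshold, at FPG up to 250 mg/dL. That is milder than the rule for a less severe peak and sits against the worst-toxicity principle in Section 6.3.1.2. A fall to Grade 3 raises no problem.

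The conclusion rests on two readings: that the post-treatment re-check covers fasting samples, since nothing in that bullet restricts it, and that keeping the dose level means here what it means in other rows.

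The consequence is one dose level and the timing of restart for a narrow group of patients. Closed enrollment and typically early onset make it likely that few remain at risk. A reader might infer a threat to the trial's results, but no endpoint, alpha, power or analysis depends on this bullet.

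**What to change.** Replace the one Grade 4 bullet with wording such as: *If the grade improves on re-check, follow the Grade 3 recommendations for hold, monitoring, restart (FPG 160 mg/dL or less, one dose level lower) and the 21-day stop. If the initial value was non-fasting or explained by a confounding factor, follow the row for the re-checked grade.*

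Pointing to the Grade 3 row is better than writing a separate restart rule. It leaves the Grade 4-to-Grade 3 route as it is and gives a single restart dose. It also carries over the 21-day stop; relying on the general 28-day limit on dose delays would give the worse event a looser limit than Grade 3.

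The cost is one bullet at the next amendment. No assessment is added beyond monitoring the Grade 3 row already prescribes, since fasting status and the 24-hour re-check are already required. The downside is an occasional extra hold or one-level reduction, and for a patient already at 200 mg, discontinuation.

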14. Patient has a known history of Human Immunodeficiency Virus (HIV) infection (testing not mandatory)
15. Patient has any other concurrent severe and/or uncontrolled medical condition that would, in the investigator's judgment, contraindicate patient participation in the clinical study (e.g. chronic active hepatitis, severe hepatic impairment, etc.)
16. Patient has currently documented pneumonitis (chest CT scan performed at baseline for the purpose of tumor assessment should be reviewed to confirm that there are no relevant pulmonary complications present).
17. Patient has clinically significant, uncontrolled heart disease and/or recent cardiac events including any of the following:
 - History of angina pectoris, coronary artery bypass graft (CABG), symptomatic pericarditis, or myocardial infarction within 12 months prior to the start of study treatment
 - History of documented congestive heart failure (New York Heart Association functional classification III-IV)
 - Documented cardiomyopathy
 - Patient has a Left Ventricular Ejection Fraction (LVEF) $<$ 50% as determined by MUGA scan or ECHO
 - History of any cardiac arrhythmias, (e.g. ventricular tachycardia), complete left bundle branch block, high grade AV block (e.g. bifascicular block, Mobitz type II and third degree AV block), supraventricular, nodal arrhythmias, or conduction abnormality in the previous 12 months.

- Uncontrolled hypertension defined by a Systolic Blood Pressure (SBP) \geq 160 mmHg and/or Diastolic Blood Pressure (DBP) \geq 100 mm Hg, with or without anti-hypertensive medication. Initiation or adjustment of antihypertensive medication(s) is allowed prior to screening.
- Long QT syndrome, family history of idiopathic sudden death or congenital long QT syndrome, or any of the following:
 - Risk factors for Torsades de Pointe (TdP) including uncorrected hypokalemia or hypomagnesemia, history of cardiac failure, or history of clinically significant/symptomatic bradycardia
 - Concomitant medication(s) with a known risk to prolong the QT interval and/or known to cause TdP that cannot be discontinued or replaced by safe alternative medication
 - Bradycardia (heart rate $<$ 50 at rest), by ECG or pulse.
 - On screening, inability to determine the QTcF interval on the ECG (i.e.: unreadable or not interpretable) or corrected QT (QTcF) $>$ 450 msec for males and $>$ 460 msec for females (using Fridericia's correction). All as determined by screening ECG (mean of triplicate ECGs).

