* Note: If total bilirubin > 3.0 x ULN is due to the indirect (non-conjugated) component only, and hemolysis as the etiology has been ruled out as per institutional guidelines (e.g. review of peripheral blood smear and haptoglobin determination), then ↓ 1 dose level and continue treatment at the discretion of the investigator.	

Dose Modifications for alpelisib/placebo as specified below. Fulvestrant may be continued while alpelisib/placebo dose is being held, at the investigators discretion, and as specified in Section 6.3.1	
Worst toxicity -CTCAE Grade (value)	Dose Modifications for alpelisib/placebo
Investigations (Cardiac)	
Cardiac – QTc prolongation	
QTcF > 500 ms (\geq Grade 3) or > 60 ms change from baseline on at least two separate ECGs	
First Occurrence:
 
 1. Assess the quality of the ECG recording and the QT value and repeat if needed 2. Interrupt study treatment 3. Determine the serum electrolyte levels (in particular hypokalemia, hypomagnesemia). If abnormal, correct abnormalities before resuming study drug treatment. 4. Review concomitant medication use for other causes for QT prolongation (refer to crediblemeds.org for known QT prolonging drugs), and for drugs with the potential to increase the risk of drug exposure related QT prolongation 5. Check study drug dosing schedule and treatment compliance 6. Consider collecting a time-matched PK sample and record time and date of last study drug intake. 
After confirming ECG reading at site, if QTcF > 500 ms or > 60 ms change from baseline
 
 • Interrupt study treatment • Repeat ECG and confirm ECG diagnosis by a cardiologist 
If QTcF confirmed > 500 ms or > 60 ms change from baseline
 
 • Correct electrolytes, eliminate culprit concomitant treatments, and identify clinical conditions that could potentially prolong the QT • Consult with a cardiologist (or qualified specialist) • Increase cardiac monitoring as indicated, until the QTcF returns to \leq 480 ms or < 60ms change from baseline. • After resolution to \leq 480 ms /60 ms change from baseline, consider re-introducing treatment at reduced dose, and increase ECG monitoring • If QTcF remains \leq 500 ms/60 ms change from baseline after dose reduction, continue planned ECG monitoring during subsequent treatment • If QTcF recurs > 500 ms/60 ms change from baseline after dose reduction, discontinue patient from alpelisib/placebo.

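### In Table 6-3 some QTcF values meet both the interruption trigger and the return criterion, and an undefined slash leaves the re-introduction, continue and discontinue bullets open to conflicting readings

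*Protocol*

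**What the plan says.** All the lines at issue are in protocol Section 6.3.1.2, Table 6-3, in the row on QTc prolongation.

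- **Trigger.** The row applies to QTcF above 500 ms "or > 60 ms change from baseline on at least two separate ECGs". The cell repeats the limits before a second instruction to interrupt: "After confirming ECG reading at site, if QTcF > 500 ms or > 60 ms change from baseline".
- **Return criterion.** Once the finding is confirmed, cardiac monitoring is increased until QTcF returns to at most "480 ms or < 60ms change from baseline".
- **Re-introduction.** After resolution to at most "480 ms /60 ms change from baseline, consider re-introducing treatment at reduced dose".
- **Continue.** If QTcF remains at or below "500 ms/60 ms change from baseline after dose reduction, continue planned ECG monitoring during subsequent treatment".
- **Discontinue.** "If QTcF recurs > 500 ms/60 ms change from baseline after dose reduction, discontinue patient from alpelisib/placebo".

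The first two use an explicit *or*; the last three use a slash. No footnote or other section says what the slash means, or that a return limit applies only to the patient who triggered on the matching limit.

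Section 5.3 (criterion 17) excludes men with screening QTcF above 450 ms and women above 460 ms, on the mean of triplicate ECGs. Section 7.2.2.7.1 makes that average the baseline.

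**The concern.** A trigger and the criterion that ends it should not both be true of the same measurement. Here an *or* trigger is paired with an *or* return criterion, so a patient who triggers on one limit can already satisfy the other limit of the return test. The three later bullets then depend on a slash that each site must interpret for itself.

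This row governs both patient safety and continued study drug. Section 6.3.1.2 makes the discontinuations in Table 6-3 mandatory and bars re-escalation after a dose reduction. Two sites with the same ECG could act differently, and each could point to the text.

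The same table is more exact elsewhere. The LVEF row directly below defines resolution by conditions that must all hold, joined by *and*.

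**Working it through.** The plan gives no figure to reproduce; this checks the logic of the rule. Let B be baseline QTcF and Q the on-treatment QTcF, in ms, with change Q − B taken as an increase.

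**Step 1. Trigger and return criterion, both with the explicit *or*.**

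- Trigger: Q > 500 or Q − B > 60.
- Return: Q ≤ 480 or Q − B < 60.

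Both hold together in one of four ways:

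1. Q > 500 and Q ≤ 480: impossible.
2. Q − B > 60 and Q − B < 60: impossible.
3. Q − B > 60 and Q ≤ 480, so B + 60 < Q ≤ 480. This needs B < 420.
4. Q > 500 and Q − B < 60, so 500 < Q < B + 60. This needs B > 440.

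In whole milliseconds:

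| Baseline | Values meeting both | Source |
|---|---|---|
| 380 | 441–480 | case 3 |
| 400 | 461–480 | case 3 |
| 410 | 471–480 | case 3 |
| 420–441 | none | – |
| 445 | 501–504 | case 4 |
| 450 (upper limit, men) | 501–509 | case 4 |
| 460 (upper limit, women) | 501–519 | case 4 |

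Two examples:

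- B = 400, Q = 465: 465 − 400 = 65 > 60, so the trigger is met; 465 ≤ 480, so the return criterion is met.
- B = 460, Q = 515: 515 > 500, so the trigger is met; 515 − 460 = 55 < 60, so the return criterion is met.

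Not every triggering value overlaps. With B = 430 and Q = 495, the change is 65, so the trigger is met; but 495 > 480 and 65 is not below 60, so the return criterion is not.

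**Step 2. The slash bullets, for the same two examples.** The 60 ms limit in the continue bullet is taken as ≤ 60.

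| Bullet | Slash read as | 400 → 465 (+65) | 460 → 515 (+55) |
|---|---|---|---|
| Re-introduction | or | met (465 ≤ 480) | met (55 < 60) |
| Re-introduction | and | not met (65 > 60) | not met (515 > 480) |
| Continue | or | met (465 ≤ 500) | met (55 ≤ 60) |
| Continue | and | not met (65 > 60) | not met (515 > 500) |
| Discontinue | or | met (65 > 60) | met (515 > 500) |
| Discontinue | and | not met (465 ≤ 500) | not met (55 ≤ 60) |

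If the slash has one meaning throughout, *or* puts these values in both the continue and the discontinue bullet, and *and* puts them in neither. The two bullets divide all values cleanly only if the slash means *or* in one and *and* in the other.

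**Step 3. Whether the examples are special.** All whole-millisecond pairs were enumerated, with baseline from 350 ms (an assumed lower limit) to the eligibility ceiling and Q from baseline to 600 ms. There are 2,530 overlapping pairs for men and 2,675 for women. With the slash as *or*, all of them meet both the continue and the discontinue bullet. With the discontinue slash as *and*, none meets that bullet. With the re-introduction slash as *and*, no pair meets both the trigger and re-introduction.

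**The case against.** The strongest reply is that the explicit *or* sits in the bullet on how long to intensify monitoring, whereas restarting drug is governed by the next bullet, which has the slash. If that slash means *and*, nobody restarts while still meeting the trigger. The last two bullets also look like intended complements, which argues against reading both slashes as *or*. This stands as evidence of intent. It does not remove the overlap between trigger and return criterion, and it requires a slash that changes meaning between adjacent bullets without saying so.

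Second, the verbs imply real change: QTcF must return, resolve, remain or recur. A value that was never above 480 ms cannot return to it. That is fair, but the numeric limits do not enforce it.

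Third, there are safeguards. The trigger needs two separate ECGs. A cardiologist confirms the finding, a cardiologist or other qualified specialist is consulted, and electrolytes and culprit drugs are dealt with. Re-introduction is only to be considered, and Section 6.3.1.2 leaves each patient's management to clinical judgment. All of this stands, and it makes the sequence possible rather than automatic.

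Fourth, the ranges count milliseconds, not patients. The documents give no frequency of such values, the predicted half-life of 8 to 9 hours (Section 1.2.2.3) makes an unchanged value off drug less plausible, and enrollment ended in July 2017. This limits the practical reach of the point.

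A reader might go further and infer that one unchanged ECG forces permanent discontinuation. The documents do not support that. The discontinue bullet is reached only after a discretionary restart, it speaks of recurrence, it depends on how the slash is read, and it lacks the word *permanently* that other rows of the table use.

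**Conclusion.** The point holds as an internal inconsistency in a safety rule. The overlap between trigger and return criterion follows from the explicit *or* in both lines and needs no further assumption. It affects any baseline below 420 ms and, in whole milliseconds, baselines from 442 ms to the eligibility ceiling.

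The consequences in the later bullets are conditional. Only if the slash is read as *or* can an overlapping value, including one above 500 ms, count as resolved for considering re-introduction, and then meet both the continue and the discontinue bullet after dose reduction. The text neither adopts nor excludes that reading.

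How many patients could be affected cannot be derived from the documents. The point merits correction because the rule is mandatory in part and the ambiguity is plain. It does not show that any patient was mismanaged.

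**What to change.** The sponsor's medical team should reconcile the trigger, monitoring/return, re-introduction, continue and discontinue bullets of the QTc row so that:

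- no QTcF value meets both the trigger and the return criterion;
- no QTcF value meets both the continue and the discontinue criterion;
- the meaning of the slash is stated wherever it is kept.

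Which thresholds and connectors achieve this is a clinical decision for the sponsor, and none is proposed here. A connector is not a neutral edit: changing the one in the trigger, for example, would change who is interrupted. The revised row can be tested with the enumeration above before release. The cost is rewording a few bullets in one table row.
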